The NICHD National Reproductive Medicine Network will conduct a multicenter randomized controlled trial to evaluate the efficacy of ovulation induction with human menopausal gonadotropin (hMG) and intrauterine insemination (IUI) -- compared to intracervical insemination (ICI), a surrogate for timed vaginal intercourse -- in the treatment of infertile couples when the female partner appears to be normal and the male partner has at least some motile sperm. The particular hMG to be used in the trial is Metrodin, a drug similar to Pergonal. In order to avoid selection by socioeconomic status, patients will not be required to pay out-of-pocket for tests or treatments related to the trial. Couples enrolled will receive up to four cycles of treatment. Insofar as possible, these will be consecutive cycles; however, rest cycles may be required for clinical indications and, in addition, subjects will be allowed up to two rest cycles for personal reasons.

The trial will enroll a total of 932 couples who have failed to conceive after a year of trying and have received no previous treatment with hMG or intrauterine insemination. Couples who meet the eligibility requirements after completing a full evaluation (described below in Section 4) will be randomly assigned to one of four treatment groups:

- 1) Intracervical insemination (control group)
- 2) Intrauterine insemination
- 3) hMG with intracervical insemination
- 4) hMG with intrauterine insemination

Randomization will occur within a Reproductive Medicine Unit (RMU), to ensure a balance of treatments at each site. Only couples who agree to be randomized can be enrolled in the study.

Each couple will undergo up to four cycles of therapy. Rates of conception, complications, and treatment failures will be determined for the four groups at each RMU.

Five statistical comparisons will be made: rates of outcomes in each of the treatment groups will be compared to the rates in the control group. In addition, in order to evaluate the relative efficacy of IUI and hMG, the group receiving IUI with hMG will be compared to the group receiving ICI with hMG and to the group receiving IUI without hMG. The Bonferroni adjustment for multiple comparisons will be made, so each test will be performed at the $0.05/5 = 0.01$ significance level.

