ICI will be carried out within 1 1/2 hours of the time of semen collection. Patients will be placed in the dorsal lithotomy position and a speculum will be used to expose the cervix. A sample of cervical mucus will be collected and evaluated for spinnbarkeit, ferning and cellularity. The presence of sperm in the mucus will be recorded. The entire remaining semen specimen will be delivered to the cervix using a sterile 18 gauge angiocatheter. Patients will remain supine for 10 minutes.

Insofar as is possible, all the inseminations at an RMU should be performed by the same person, with one other person covering on weekends. Quality control of the IUI and ICI procedures is discussed in Section 8 below, under Responsibilities of the Reproductive Medicine Units.

D. Sample Size

We hypothesize that the pregnancy rate in the control group (no hMG/ICI) for this revised study will be a weighted average of the hypothesized control pregnancy rates in the two earlier populations --- 10% for the couples with unexplained infertility and 5% for couples with male factor infertility. Based on the enrollment experience of the RMUs, and on a desire to be conservative, we project that 50% of the combined population will be from the unexplained infertility group and that 50% will be from the male factor infertility group. The overall control pregnancy rate is therefore hypothesized to be $0.50 \times 0.10 + 0.50 \times 0.05 = 0.075$.

There will be three statistical comparisons in which each of the experimental groups (no hMG/IUI, hMG/IUI and hMG/ICI) is compared to the control group (no hMG/ICI). In

addition, two other pairwise comparisons will be made (hMG/IUI versus no hMG/IUI and hMG/IUI versus hMG/ICI). In order to correct for the increased chances of finding statistical significance solely because of the multiplicity of comparisons being performed, the Bonferroni test criterion will be employed: each of the primary comparisons will be tested at the significance level of $0.05/5 = 0.01$ using a two-tailed test. That is, a critical ratio must exceed 2.576 instead of 1.96 in order for the corresponding comparison to be declared statistically significant with an overall error rate of 0.05.

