Every six months, the DCC will provide the Steering Committee with aggregate summaries of the data collected to date. On the recommendation of the DSMB, which will

have access to data broken down by treatment group, the Steering Committee will decide whether to continue the study or to terminate it. These decisions will seriously affect the operating characteristics of the study (significance level and power), and should therefore be made according to rules developed for performing interim analyses of accumulating data (Friedman et al., 1985: Chapter 15; Pocock, 1983: Chapter 10).

The possibility must be entertained that one of the experimental treatments is less effective than the control. If this seems to be the case based on the interim data, and if harm to the patient is possible, the Steering Committee should be encouraged to decide on early termination of that treatment arm with less persuasive evidence than required for early termination with a positive conclusion (Lan and Friedman, 1986). That is, the Steering Committee might decide to drop an investigational regimen with the conclusion that it may be poorer than the control if the p-value for the test comparing the two is 0.15 or less.

The most widely used procedure for performing several interim statistical analyses while holding the overall significance level at the usual value (0.05 or 0.01) is the one due to O'Brien and Fleming (1979). This procedure will be adopted for interim analyses aimed at testing for efficacy.

E. Methods of analysis

The unit of analysis will be the couple, and the primary response variable will be a binary one: success if the woman conceives while in the study versus failure if not. The most important principle underlying the statistical analysis will be the intention-to-treat principle. It is characterized by the aphorism "If randomized, analyzed": a couple who has been randomized to a treatment group is analyzed along with all other couples so randomized, even if they were minimally compliant. This principle leads to a likely underestimation of a

treatment's effect, but the alternative of removing minimally compliant or noncompliant couples could lead to the worse bias of overestimating its effect. For example, a couple's decision to discontinue complying with the assigned treatment regimen might be due to a perceived lack of efficacy. The withdrawal of such a couple from analysis could result in an overestimation of that treatment's effectiveness.

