The primary statistical analysis will consist of separate comparisons of each experimental treatment's success rate versus the control's after stratifying on RMU using the Mantel-Haenszel chi-square procedure (1959). If other variables measured at baseline are found to be distributed very differently in different treatment groups (the criterion for "very different" might be statistical significance at the 0.10 or 0.20 level), they would be adjusted for statistically, either by post-stratification (using the Mantel-Haenszel procedure) or by regression control (using logistic regression modeling) in a secondary, confirmatory analysis. Given the likelihood that these variables will be only slightly correlated with response, the results of the secondary analysis will almost surely confirm the results of the primary one, with respect both to the direction of the difference between the treatments and to its statistical significance or nonsignificance. In the extremely unlikely event that the results of the primary and secondary analyses are contradictory, there would be little if any credibility to any attempted definitive inference from the study.

References

4. Daly DC. Treatment validation of ultrasound-defined abnormal follicular dynamics as a cause of infertility. *Fertil Steril* 1989; 51:51.

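### Section 9E's primary analysis names three of the five primary comparisons, and the 2.576 cut-off does not allow for the O'Brien-Fleming looks adopted in Section 9D

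*Protocol*

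**What the plan says.** Section 2 (Overview) announces the family: "Five statistical comparisons will be made". These are three experimental arms against control, plus hMG/IUI against each of its two components, with a Bonferroni level of 0.05/5.

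Section 3D (Sample Size) repeats this. After the three tests against control, "two other pairwise comparisons will be made (hMG/IUI versus no hMG/IUI and hMG/IUI versus hMG/ICI"). It then states that "each of the primary comparisons will be tested at the significance level of $0.05/5 = 0.01$ using a two-tailed test", and that "a critical ratio must exceed 2.576 instead of 1.96 in order for the corresponding comparison to be declared statistically significant".

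Section 9E (Methods of analysis) describes the primary set differently: "The primary statistical analysis will consist of separate comparisons of each experimental treatment's success rate versus the control's after stratifying on RMU", using Mantel-Haenszel. It gives no significance level and does not mention the two comparisons between active arms.

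Section 9D (Interim analyses) introduces O'Brien-Fleming as the most widely used way of testing repeatedly "while holding the overall significance level at the usual value (0.05 or 0.01"), and then says: "This procedure will be adopted for interim analyses aimed at testing for efficacy". It gives neither the number of efficacy looks nor the level to be held for each of the five comparisons, and it does not return to 2.576.

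**The concern.** A decision rule needs three things to agree: which hypotheses are primary, at what level each is tested, and what critical value applies at the last analysis. Here they do not fully agree.

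First, the status of the two between-treatment comparisons is open. In Section 3D they are primary and take two fifths of the Bonferroni allowance. In Section 9E they are absent from the primary analysis and have no named test. They answer whether the combination beats either component alone, so a reader of the results should know in advance whether they are confirmatory.

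Second, Section 3D gives 2.576 without qualification. That is the two-sided 0.01 point for a single analysis. Once efficacy looks are taken with an O'Brien-Fleming boundary, the last look needs a somewhat higher value to keep 0.01 per comparison. Someone following Section 3D and someone following Section 9D could judge the same borderline result differently.

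**Working it through.** **1. The plan's own figures.** Inputs from Section 3D: rates 0.075 and 0.1875, two-sided 0.01 (z = 2.576), power 80% (z = 0.842), equal arms. The pooled formula without continuity correction is

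n = [z_α √(2 p̄(1−p̄)) + z_β √(p₁(1−p₁) + p₂(1−p₂))]² / (p₂−p₁)²

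- p̄ = (0.075 + 0.1875)/2 = 0.13125, and √(2 × 0.13125 × 0.86875) = 0.4775
- √(0.0694 + 0.1523) = 0.4709
- n = (2.576 × 0.4775 + 0.842 × 0.4709)² / 0.1125² = 1.626² / 0.01266 ≈ 209, against 210 stated.

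Power at 210 per arm for 0.10 versus 0.20: (0.10 × √210 − 2.576 × 0.5050)/0.5 = 0.297, which is 61.7%, against 62% stated. For 0.075 versus 0.1875 the same calculation gives 80.2%. The sample size is therefore right for five tests at 0.01 in a design with no interim looks.

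**2. The primary set, section by section.**

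| Comparison | Sections 2 and 3D | Section 9E primary analysis |
|---|---|---|
| IUI vs ICI | yes, 0.01 | yes, no level given |
| hMG/ICI vs ICI | yes, 0.01 | yes, no level given |
| hMG/IUI vs ICI | yes, 0.01 | yes, no level given |
| hMG/IUI vs IUI | yes, 0.01 | not named |
| hMG/IUI vs hMG/ICI | yes, 0.01 | not named |

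**3. The final cut-off with O'Brien-Fleming at 0.01 per comparison.** The boundary at look k of K is c√(K/k), so the final value is c. It is solved by recursive numerical integration so that the total two-sided crossing probability is 0.01. Equal spacing and the number of looks are assumptions. Section 9D's six-monthly schedule is for aggregate summaries, not stated efficacy looks.

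| Looks | Final value c | Per-test error if the last look uses 2.576 |
|---|---|---|
| 2 | 2.580 | 0.0101 |
| 3 | 2.595 | 0.0105 |
| 4 | 2.609 | 0.0109 |
| 6 | 2.631 | 0.0113 |
| 8 | 2.648 | 0.0116 |

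The Bonferroni bound over five tests becomes 5 × 0.0101 ≈ 0.051 to 5 × 0.0116 = 0.058. The bound ignores the correlation between contrasts that share arms. Simulating the five correlated contrasts under the global null, with O'Brien-Fleming bounds at the interim looks and 2.576 at the end, gives a family-wise error of about 4.3%, 4.6%, 4.8% and 4.9% for 2, 4, 6 and 8 looks.

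If the raised cut-off is applied at the final analysis alone, power for 0.075 versus 0.1875 falls from 80.2% to 80.1% (2 looks) or 78.2% (8 looks).

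**4. Holm instead of single-step Bonferroni.** Simulation of 400,000 four-arm trials, 210 per arm, pooled z-tests, no interim looks, rates 0.075/0.10/0.10/0.20 for ICI, IUI, hMG/ICI and hMG/IUI:

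- each 0.10 versus 0.20 test: 62% with Bonferroni, 68% with Holm
- hMG/IUI versus control: 89% and 90%
- at least one rejection: 93.7% with both, because Holm's first step is still 0.05/5.

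Under the global null the family-wise error is the same for both: 0.040 at a common rate of 0.075 and 0.042 at 0.15.

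**The case against.** The strongest reply is that little here is wrong. Sections 2 and 3D agree on five comparisons at 0.01, and Section 9E states no rival level. Testing its three comparisons at 0.01 is valid and, if they were the whole family, conservative. A reader might infer that Section 9E implies dividing by three, with a lower cut-off of 2.394 and more power. The protocol states no such level or cut-off, so that is conjecture.

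A reader might also infer from "holding the overall significance level at the usual value (0.05 or 0.01") that each comparison could be tested at 0.05 with family-wise control lost. The sentence describes the method in general. Sections 2 and 3D set 0.01 for this trial, and no section proposes 0.05 per comparison.

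On the cut-off, 2.576 can be read as the fixed-design translation of 0.01 in a sample-size section. Because the contrasts are correlated, keeping it at the last look left simulated family-wise error just under 5% for up to 8 looks. Finally, Bonferroni is a valid, prespecified choice, and Section 3D itself calls the power for the between-treatment difference moderate.

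Most of this stands, and it limits the point to a modest one. It does not settle whether the two between-treatment comparisons are primary, since two sections of the same document answer differently. Nor does it remove the mismatch between an unqualified 2.576 and a group-sequential boundary.

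**Conclusion.** The primary set is stated inconsistently: five comparisons in Sections 2 and 3D, three in Section 9E's primary analysis. This is the main part of the point. It affects the standing of the conclusions about the combination against its components, not the sample size.

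The 2.576 cut-off is slightly too low for a group-sequential test at 0.01 per comparison. For an assumed 2 to 8 equally spaced looks the final value is 2.580 to 2.648, and the per-test error with 2.576 is 0.0101 to 0.0116. That is a small effect, and it does not show that the trial's 5% family-wise rate is breached.

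Single-step Bonferroni is not an error. Holm would be a cheap gain of about six percentage points for the 0.10 versus 0.20 comparisons in the scenario shown. That gain was calculated without interim looks and arises only after a first rejection.

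**What to change.** **Needed clarification**

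- Name the same family of five comparisons in Sections 2, 3D and 9E, all tested by RMU-stratified Mantel-Haenszel.
- State in Section 9D that O'Brien-Fleming holds the multiplicity-adjusted level for each comparison, not 0.05, and give the planned number of efficacy looks.
- In Section 3D, replace 2.576 as the final cut-off by the O'Brien-Fleming value for the looks held, for example 2.609 for four.

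**Optional improvement**

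Use Holm over the five tests (ordered p-values against 0.05/5, 0.05/4, 0.05/3, 0.05/2, 0.05/1). One O'Brien-Fleming level of 0.01 with one final value cannot be combined with this. Each Holm level needs its own boundary, moving to the next after each rejection. For four equally spaced looks the final values are 2.609, 2.534, 2.435, 2.289 and 2.024.

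**Cost**

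The clarification is wording only and needs no more couples. Holm adds the specification of the level-by-level boundaries. Its drawback is that simultaneous confidence intervals no longer match the step-down decisions; 99% intervals can be reported alongside. All of this should be settled before the first efficacy look at data by treatment group.

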**NICHD
NATIONAL REPRODUCTIVE MEDICINE NETWORK PROTOCOL**

**Ovulation Induction/Insemination Trial
Revised Protocol, February, 1993**

DATA COORDINATING CENTER

**Columbia University
New York, NY 10032**

Preface

Initially, the Steering Committee of the NICHD National Reproductive Medicine Network proposed to evaluate the efficacy of ovulation induction with Metrodin and/or intrauterine insemination in two simultaneous randomized controlled trials, one focused on couples with unexplained infertility and the other on couples diagnosed with pure male-factor infertility. By June of 1992, 60 couples had been randomized to treatment according to this design -- 36 with unexplained infertility and 24 with pure male factor infertility.

Experience in designing and implementing the initial study protocol showed, however, that distinguishing these two diagnostic groups was problematic. The distinction was based on arbitrary cut points in the semen parameters by which male fertility potential is currently assessed, but for which intraindividual variability is fairly large. Enrollment in the two trials was lower than expected because many couples had to be excluded from both groups when they failed to meet just one of the strict inclusion criteria related to semen quality. This led to a reassessment of the literature on which the semen cut points are based and, ultimately, to the conclusion that they are not well supported and that the attempt to diagnose male factor infertility should be abandoned.

On June 15, 1992, the study design was revised in favor of a single trial which would include all infertile couples where the female partner is "normal" and the male has at least some motile sperm. The primary study question to be tested in this single trial is whether Metrodin and/or intrauterine insemination are efficacious in the treatment of the group of infertility patients fitting this broader definition. A secondary analysis will search for points along the continuum of male semen parameters that appear to influence the efficacy of treatment. Yet another set of analyses will utilize the data collected in the course of the trial, together with ancillary data on sperm parameters in fertile males, to try to identify boundaries that define male-factor infertility with more precision and accuracy than has heretofore been possible.

NICHD NATIONAL REPRODUCTIVE MEDICINE NETWORK

Revised February, 1993

Table of Contents

Section	Page
1. Introduction and Background	1

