The cumulative per-couple fecundity rate in at least one of the experimental groups is hypothesized to be 0.1875, a 2.5-fold increase over the hypothesized rate of 0.075 in the control group. With the parameters of the study as given above, and with a power of 80% to find statistical significance, the required total size is 840 couples, 210 couples per regimen (Fleiss 1981). We further hypothesize success rates of 0.10 and 0.20 in some pair of experimental regimens. The power to find significance with a sample of 210 couples per treatment group is 62%. Power is therefore moderate to detect as significant a difference between a slightly effective and highly effective test regimen.

We may wish to be conservative and assume that there is a loss of information in 10% of the couples. A total of 932 couples should therefore be randomized, 233 to each treatment group.

An issue that has to be considered is the likely inadequacy of our projected sample size for the secondary analyses of semen characteristics. Given the principle that such analyses should be performed in the study's control group, it is ironic that the pregnancy rate in the control group will likely be the lowest of all.

E. Inclusion and Exclusion Criteria

Couples of all races and ethnic origins will be eligible to enter the trials. Because of geographic location and patient demographics, the five participating RMUs will be able to provide subjects from minority groups. In addition, by adhering to the principle that patients should not have to pay out-of-pocket for tests or treatments related to the trial, there should be no selection by income.

Eligibility criteria for entrance into the trial are intentionally conservative or "strict" so that the findings will stand up to criticism. The aim is to exclude any couple with a possible "explanation" for reduced fertility in the female partner. The minimum criteria for inclusion in the study based on a standard diagnostic workup are outlined on the next page; exclusion criteria based on medical history are immediately following. In addition, Appendix C. (p. 64) is a compilation of decisions by the Clinical Subcommittee that further clarifies the inclusion and exclusion criteria.

Inclusion Criteria For Females*

1. Age 40 years or younger.
2. Pregnancy test negative.
3. Evidence of a normal pelvis and uterine cavity based on results of a laparoscopy and hysterosalpingogram (or hysteroscopy) anytime in the past.

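### Section 3D assigns the secondary semen analyses to the control arm, which cannot answer the Preface's question of which semen values change treatment efficacy

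*Protocol*

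**What the plan says.** The Preface sets two different semen aims.

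- The first concerns treatment effect: "A secondary analysis will search for points along the continuum of male semen parameters that appear to influence the efficacy of treatment".
- The second is introduced separately. It would use trial data, together with ancillary data on fertile men, to find boundaries that define male-factor infertility.

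Section 3D comes back to the semen work, calls it secondary, and warns that the sample is probably too small for it. The reason given begins "Given the principle that such analyses should be performed in the study's control group" and goes on to note that this group will probably have the lowest pregnancy rate of the four. Section 3D does not say which of the two aims it means.

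Section 9E describes the primary comparisons and the covariate-adjusted confirmatory analysis, and does not mention the semen analyses. Their details may sit in a statistical analysis plan that is not at hand, so that silence is not counted against the protocol.

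**The concern.** Efficacy in this trial is always a difference between arms: each experimental regimen against ICI, and the combined regimen against each single one (Sections 2 and 3D). Asking whether semen values influence efficacy is asking whether that difference changes with semen quality. Section 3D fixes, as a principle, an analysis group in which no such difference exists.

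An analysis plan that followed Section 3D faithfully would therefore answer a different question, namely prognosis under ICI. Its results could be misread as showing who benefits from hMG or IUI. After the redesign, couples are enrolled across the whole range of semen quality, and this analysis is where the protocol asks whether treatment works differently along that range.

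**Working it through.** **1. What each group can identify.** For regimen k and semen value x, write the effect as

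δₖ(x) = logit P(pregnant | regimen k, x) − logit P(pregnant | control, x).

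The Preface's first aim asks whether δₖ(x) changes with x. Control couples inform only the second term. Any shape of δₖ(x) is compatible with any control-arm result, because the first term is unobserved. More control couples would not change this.

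**2. The protocol's own sample-size figures reproduce.** The inputs are from Section 3D: a control rate of 0.50 × 0.10 + 0.50 × 0.05 = 0.075; an experimental rate that "is hypothesized to be 0.1875, a 2.5-fold increase over the hypothesized rate of 0.075 in the control group"; two-sided 0.01; 80% power. With mean rate p̄ = 0.13125:

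n = [2.576·√(2·0.13125·0.86875) + 0.842·√(0.075·0.925 + 0.1875·0.8125)]² / 0.1125² ≈ 2.645 / 0.01266 ≈ 209 per arm.

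The protocol has 210. At 210 per arm, power for 0.10 against 0.20 is 61.7% (stated 62%). Allowing for 10% loss, 840 / 0.9 = 933.3 (stated 932, or 233 per arm). These inputs can therefore be used below.

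**3. Expected pregnancies.** The protocol gives no count for the semen analyses.

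- Control arm: 233 × 0.075 = 17.5 (210 × 0.075 = 15.75 after losses).
- All four arms at 0.075: 932 × 0.075 = 69.9.
- Three experimental arms at 0.1875: 17.5 + 3 × 233 × 0.1875 = 148.5.
- Control share: 17.5 / 69.9 = 25% down to 17.5 / 148.5 = 12%.

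**4. What the control arm can do even for prognosis.** Section 3D assumes control rates of "10% for the couples with unexplained infertility and 5% for couples with male factor infertility". Take one cut fixed in advance that separates exactly these rates in equal halves of 233 (116.5 each), tested at two-sided 0.05:

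z = [0.05·√116.5 − 1.96·√(2·0.075·0.925)] / √(0.05·0.95 + 0.10·0.90) = (0.540 − 0.730) / 0.371 = −0.51, so power is about 30% (28% with 210).

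**5. What four arms can do for interaction (assumed rates).** Compare one experimental arm with control, 233 each, split in equal halves at a fixed cut, with control at 5% and 10% and a Wald test of the interaction log odds ratio at two-sided 0.05.

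- Experimental 10% and 27.5% (mean 0.1875): log odds ratio 0.48, standard error 0.64, power about 11%.
- Experimental 5% and 32.5% (same mean): log odds ratio 1.47, standard error 0.70, power about 55%.

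The four-arm analysis is the right one for the question, but it is not a powerful one.

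**6. Searching for a cut-point (illustration only).** This is a null simulation in 233 controls with a 7.5% pregnancy rate, comparing the largest chi-square over candidate cuts with the uncorrected 5% limit. There were 3,000–4,000 runs per setting, so the simulation standard error is below 1 percentage point.

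| Setting | False positives |
|---|---|
| One parameter, all cuts in central 80% of values | 40% |
| One parameter, all cuts in central 60% | 30% |
| One parameter, only 3 candidate cuts | 12% |
| Three parameters, correlation 0.5, central 80% | 75% |
| Three parameters, correlation 0.5, only 3 cuts each | 30% |
| Four uncorrelated parameters, central 80% | 86% |

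The protocol fixes none of these settings.

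**The case against.** **The sentence may have been meant for the other aim.** Boundaries of male-factor infertility concern fecundity without hMG or IUI. The ICI arm, which Section 2 presents as a stand-in for timed intercourse, is a natural group for that. Section 3D does not mention efficacy and speaks of analyses in the plural. This objection stands in part. Against it, the label secondary in Section 3D matches the Preface's label for the efficacy aim, and the Preface introduces the boundary work as a further set. The text is at best ambiguous. If the narrower meaning was intended, it should say so.

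**Low numbers are already admitted.** This is true, and low power alone would not be a finding. The admission concerns quantity only and does not touch the absence of a treatment contrast.

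**A reader might infer that the planned search has a 40–75% false-positive rate.** The documents do not support that. They set no test, significance level, number of parameters, range of cuts or absence of correction for these analyses, and the Preface's language is exploratory. The figures in step 6 show why selection needs adjustment; they are not a property of the plan.

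**A reader might also infer that the control-group rule should simply go, or that the semen question was the reason for merging the two trials.** Neither follows. The rule suits the boundary aim. The Preface justifies the merger by the difficulty of separating the diagnostic groups, poorly supported thresholds and slow enrollment.

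**Conclusion.** The concern holds as a conflict between the Preface and Section 3D. As written, the control-group principle covers the secondary semen analyses, and an analysis in that group cannot show which semen values modify the effect of hMG or IUI. This conclusion is logical and needs no assumption about rates.

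On the protocol's own rates, the restriction would also use about 17.5 of some 70 to 149 expected pregnancies, or 12–25%. The range reflects whether the experimental arms stay at 0.075 or all three reach 0.1875. The protocol does not give a rate for every arm, so no single fraction can be stated.

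The five primary comparisons are unaffected. The point is worth correcting because the mismatch concerns a named secondary aim and is cheap to remove.

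**What to change.** Reconcile the two places.

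- In Section 3D, limit the control-group principle to the male-factor boundary (prognostic) analyses.
- State that efficacy modification is tested in all randomized couples, with a logistic model containing RMU, treatment, each screening semen parameter as a continuous term, and its interaction with treatment. Use the pre-randomization screening values, not specimens from treatment cycles.
- If a cut-point chosen from the data is reported, give a selection-adjusted p-value, for example from permutation, and label it exploratory.
- Extend the Section 3D caution on sample size to the interaction analysis.

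No new data are needed: a screening semen sample is required of every male partner, and semen is evaluated in both the IUI and ICI procedures (Sections 3C and 3E). The cost is a few sentences and slightly more analysis. Interaction power stays limited, so a null result should not be read as evidence that efficacy is the same across semen quality.
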